3.10.2. Model recalibration

If calibration and discrimination measures of external validation demonstrate a poor fit, the model will be recalibrated and adjusted using the data of included patients. This will be done over four stages:

- Stage 1: The regression coefficients (including the intercept and slope) will be recalibrated. This will be done using a logistic regression model fitted with the linear predictor as the only covariate.
- Stage 2: The recalibrated model predictors will each be removed in a stepwise manner by a non-automated criterion-based procedure starting with the variable with a hazard ratio closest to 1. After removal of this variable, the aforementioned measures of discrimination of calibration and discrimination will be reassessed to detect model improvement. If the performance of the model is unimproved or worsens, the variable will be reintroduced to the model. This step will be repeated in a staged manner until no further improvements are detected. Introduction of new predictive variables will not be possible as data points captured in this study have been limited to predictive parameters and outcomes as per the IMPACT model.
- Stage 3: The internal validity of the updated model will be assessed using a bootstrapping method
- Stage 4: Adjusted stratification by ACCI and PS (Table 1) will be performed to achieve statistically significant differences in equality across cumulative incidence rate groups, judged by the Fine and Gray test

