- To recalibrate the prognostic model IMPACT
- To determine the growth patterns of incidental meningiomas
- To examine the MRI and pathology features of meningiomas subject to surgical resection
- To determine the risk of post-intervention complications and tumour recurrence/growth for meningiomas subject to surgery, stereotactic radiosurgery, or fractionated radiotherapy
- To assess the economic implications of stratifying follow-up according to risk of disease progression

Study design Retrospective study of longitudinal radiological and clinical outcomes of incidental intracranial meningioma patients at participating centres diagnosed between 01/01/2009 and 31/12/2010. Data will be recorded until death or last date of follow-up.

Sample size 1500 patients

STUDY FLOWCHART

[figure not shown]

TABLE OF CONTENTS

STUDY SYNOPSIS	3
STUDY FLOWCHART	4
1 INTRODUCTION	6
1.1. THE IMPACT MODEL	7
2 OBJECTIVES	7
2.1. Primary objective	7
2.2. Secondary objectives	7
3 METHODS	7
3.1. Study design	7
3.2. Study population and eligibility criteria	7
3.3. Patient identification	8
3.4. Sample size	9
3.5. Study endpoints	9
3.6. Data collection	9
3.7. REDCap database	9
3.8. Recorded variables	10
3.9. Data quality assurance	13
3.10. Planned statistical analysis	14
4 ETHICS AND DISSEMINATION	16
4.1. Study registration	16
4.2. Local investigator responsibilities	16
4.3. Confidentiality and data protection	16
4.4. Ownership	17
4.5. Dissemination of results	17
4.6. Authorship eligibility	17
5 FUNDING	17
6 STUDY TIMELINE	18
7 CONCLUSION	18
8 REFERENCES	18
9 APPENDICES	20

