1.1. THE IMPACT MODEL

The model, based on MRI parameters, stratifies patients with an incidental meningioma into three risk groups: low-, medium- and high-risk. These MRI parameters are as follows: meningioma volume, meningioma hyperintensity, peritumoral signal change and proximity to critical neurovascular structures. This predictive function was built using an internally validated cox regression model. Patients were also stratified in the model based on age, comorbidity and performance status using competing risk analyses.

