3.10. Planned statistical analysis

3.10.1. External validation

Using IMPACT, the five- and ten-year estimated risk of disease progression for every patient included in this cohort study will be calculated. Kaplan-Meier method will be used to obtain the observed risks. The predictive performance of IMPACT will be assessed by examining measures of calibration and discrimination. Calibration refers to how closely the predicted 5- and 10-year risk of progression agrees with the observed risk. A calibration plot compares the observed and predicted rates of events for each group. A perfect match indicates accurate calibration. The Brier score for censored survival data will also be calculated, which is a measure of accuracy and is the average squared deviation between predicted and observed risk; a lower score represents greater accuracy. Discrimination is the ability of the risk score to differentiate between those patients who do and those who do not experience disease progression during the study timeframe. This measure is quantified by calculating the C-statistic, D-statistic and Chambless and Diao's time-dependent AUC (area under the receiver operating characteristic curve [ROC]) which are tailored towards censored survival data. Model assumptions will be tested by examination of Schoenfeld residuals, and influential observations will be examined using DFBETA panels.

The effect of patient age, comorbidity, and performance status on the risk of disease progression and intervention will be assessed using a competing risk analysis. Patients will be split based on WHO PS into two categories: 0-1 and 2-4 and stratified by ACCI (Table 1) into three groups: 0-2, 3-5 and ≥ 6 . An ACCI score of ≤ 2 corresponds to patients who are young (<60 years) with few or no comorbidities. An ACCI score of 3–5 corresponds to either an older patient with few comorbidities, or a younger patient with several comorbidities, and an ACCI score ≥ 6 denotes older patient with comorbidities (24).

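### One trigger, misfit of the predicted progression risk, governs all four update stages: no re-check follows Stage 1, and the PS/ACCI grouping has no trigger of its own

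*Protocol*

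**What the plan says.** Section 1.1 describes two parts of IMPACT. One is a Cox risk function built on MRI parameters. The other is a stratification by patient factors: "Patients were also stratified in the model based on age, comorbidity and performance status using competing risk analyses".

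Section 3.10.1 assesses them differently.
- **Risk function:** "The predictive performance of IMPACT will be assessed by examining measures of calibration and discrimination", and "Calibration refers to how closely the predicted 5- and 10-year risk of progression agrees with the observed risk". The listed tools are a calibration plot, a Brier score for censored data, the C-statistic, the D-statistic and a time-dependent AUC.
- **PS/ACCI groups:** cumulative incidence curves with confidence intervals, a Fine and Gray test of equality, and a comparison with the training data. No action is attached to that comparison.

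Section 3.10.2 then sets one condition, "If calibration and discrimination measures of external validation demonstrate a poor fit, the model will be recalibrated and adjusted", followed by "This will be done over four stages". Stage 1 recalibrates intercept and slope. Stage 2 removes predictors one at a time and puts a predictor back if performance is unimproved or worse. Stage 3 bootstraps the updated model. Stage 4 turns to the patient groups: "Adjusted stratification by ACCI and PS (Table 1) will be performed", with the aim of significant differences on the Fine and Gray test.

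The secondary objective in section 2.2 is conditional in the same way. The synopsis lists it without a condition: "To recalibrate the prognostic model IMPACT".

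**The concern.** An update rule should act on the part that failed and stop once the fault is repaired. Here a single gateway, defined on the risk function, controls changes to both parts, and no exit is written between the stages.

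Updating the model is a stated secondary objective. Under the present rule, a model that needed only a shift in baseline risk could go on to lose a true predictor. A PS/ACCI grouping that replicated could be redrawn, and one that failed to replicate could be left in place. The primary objective, external validation, is not at risk.

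**Working it through.** **1. Plan's own figure.** Section 3.4 asks for 100 events at a 10% progression risk: 100 / 0.10 = 1000 patients, which reproduces. The minimum of 1500 gives 1500 × 0.10 = 150 events, or 100 events if the risk is 100 / 1500 = 6.7%. This sets the event range for step 4; it does not itself bear on the trigger.

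**2. What the condition leads to.** The word joining calibration and discrimination can be read as needing both faults or either one.

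| Finding at validation | Both faults needed | Either fault enough |
|---|---|---|
| Calibration poor, discrimination good | No update | All four stages |
| Calibration good, discrimination poor | No update | All four stages |
| Both poor | All four stages | All four stages |
| Both good, PS/ACCI incidences differ from training | No update | No update |

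On the first reading, a model with only a wrong baseline risk is never recalibrated. On the second, it is recalibrated and then passes to Stage 2 unchecked. The last row has no route to an update on either reading.

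**3. What Stage 1 can repair.** It replaces the linear predictor LP by a + b × LP. With b > 0 the ranking of patients is unchanged, so discrimination is too. In simulation the C-statistic moved by at most 0.0035, through tie rounding. Stage 1 can therefore be sufficient for a pure calibration fault, and Stage 2 is a reasonable next step only where discrimination is inadequate.

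**4. How often Stage 2 would drop a true predictor that should stay.** The protocol gives no effect sizes or prevalences, so all of those below are assumptions. The published weights are taken as exactly right, and only the first removal is examined.

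*Binary outcome, no censoring.* N = 1500, 10% risk, four binary predictors each at 35% prevalence, the other three ORs 2, 2.5 and 3, published odds doubled by an intercept error, 600 runs. Stage 1 was applied, the predictor with the smallest coefficient was removed, and the reduced model was rescaled and compared.

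| Weakest true OR | C-statistic and Brier both improve | C-statistic alone | Brier alone |
|---|---|---|---|
| 1.2 | 14% | 24% | 27% |
| 1.5 | 6% | 8% | 17% |

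Monte Carlo error for the 14% figure: √(0.14 × 0.86 / 600) = 1.4 percentage points.

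*Survival outcome.* N = 1500, one continuous predictor (log HR 0.6), binary predictors with log HR 0.8, 0.7 and log(1.2, 1.3 or 1.5) at prevalences 30%, 12% and 40%, exponential dropout with mean 10 years, and follow-up ending at 10.1 to 12.5 years. Runs had about 100 to 165 events.

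| Weakest true HR | C-statistic and 5- and 10-year Brier all improve (two runs) | C-statistic alone (three runs) |
|---|---|---|
| 1.2 | 15%, 15% | 33%, 35%, 36% |
| 1.3 | 8%, 7% | 26–29%, 26%, 24% |
| 1.5 | 3%, 6% | 15–19%, 12%, 17% |

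**5. What Stage 4 tests.** Its criterion is significance, at the 0.05 level given in section 3.10.3. Agreement with the training data is a different question. Groups whose incidences match the training data but miss P < 0.05 would meet the Stage 4 reason for adjustment.

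**The case against.** Several counter-arguments have force, and they limit the point.

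- **Put-back rule.** A reader might infer that predictors are stripped automatically once Stage 1 is done. The text does not support that: trial removal is automatic, permanent removal is not. The rule also does useful work. In the binary simulation it dropped a predictor with no true effect (published OR 1.5) in 66% of runs. But it states no margin of improvement and no rule for measures that disagree, so chance losses remain. A predictor whose removal worsens none of the measures is also a small loss.
- **Stage 4 may be idle.** A reader might infer that misfit of the risk function always redraws the PS/ACCI groups. If the existing groups already differ significantly, Stage 4 can be read as having nothing to do. The defect remains for groups that replicate without reaching significance.
- **Conjunctive trigger.** If both faults are needed, a pure baseline shift never reaches Stage 2. That removes the predictor-loss problem for this case, but leaves the miscalibrated model without recalibration.
- **Broad reading of the model.** Section 1.1 places the patient factors in the model, and section 2.2 speaks generally of external validation measures. The operative condition in 3.10.2 is narrower, and the measures it names do not test PS/ACCI.
- **Likelihood of a baseline shift.** It is tempting to call this a probable failure because section 3.4 expects the progression risk to vary. That sentence is a sample-size allowance and shows only that a shift is possible.
- **Detail for a later plan.** Operating rules are often deferred. Here the protocol fixes the sequence and its condition, so the rule is stated, and section 3.10.3 provides for a review before final analysis.

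**Conclusion.** The point holds as a flaw in the update rule for a secondary objective. That one condition governs all four stages, that no re-check follows Stage 1, and that no route leads from a failed PS/ACCI comparison to an update all follow from the text without any assumption.

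The size of the predictor loss does rest on assumptions about effects and prevalences. For a weakest true HR or OR of 1.2 to 1.5 and about 100 to 165 events, it is roughly 3–15% of datasets when C-statistic and Brier score must both improve. On the C-statistic alone it is about 12–36% with survival data and 8–24% in the binary version. The joint criterion is closer to the plan, which reassesses both calibration and discrimination. Stage 2 is repeated, so these first-step figures do not cover later removals. The effect on PS/ACCI is a matter of decision logic and has no percentage attached.

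The synopsis wording is a minor alignment and carries none of this conclusion.

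**What to change.** Amend section 3.10.2 as follows.

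1. State that poor calibration alone, or poor discrimination alone, is enough to start Stage 1.
2. After Stage 1, repeat the calibration and discrimination measures. If calibration was the only fault and is now corrected, stop.
3. Enter Stage 2 only if discrimination remains inadequate.
4. Detach Stage 4 from this sequence. Trigger it only when the observed PS/ACCI cumulative incidences disagree with the training-set values, using the comparison already planned in section 3.10.1.

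Also align the synopsis objective with section 2.2. The cost is a few sentences and one extra reassessment after Stage 1. No new data are needed.

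### Stage 1 recalibrates a Cox model by ordinary logistic regression, with no horizon or rule for patients whose follow-up ends early

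*Protocol*

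**What the plan says.** Section 1.1 describes the model under test: "This predictive function was built using an internally validated cox regression model". Section 3.10.1 fixes the quantity it predicts: "Using IMPACT, the five- and ten-year estimated risk of disease progression for every patient included in this cohort study will be calculated". The validation tools in that section suit such a model. For the comparison, "Kaplan-Meier method will be used to obtain the observed risks"; for accuracy, "The Brier score for censored survival data will also be calculated"; and the discrimination measures are ones "which are tailored towards censored survival data".

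Section 3.10.2 applies only if validation shows poor fit. Stage 1 there reads "The regression coefficients (including the intercept and slope) will be recalibrated", and then "This will be done using a logistic regression model fitted with the linear predictor as the only covariate". Stage 2 removes predictors from the recalibrated model one at a time, "starting with the variable with a hazard ratio closest to 1".

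The synopsis and sections 3.8.4 and 3.10.1 show that follow-up length varies. It ends at discharge, loss to follow-up, death or the last clinic visit. Section 3.4 raises the sample size partly to allow for loss to follow-up.

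**The concern.** A logistic model needs a yes/no outcome for every patient at a fixed time. Stage 1 names no time and does not say how to classify a patient last seen, progression-free, before year 5 or year 10. Ordinary logistic regression leaves two options: call that patient a non-event, or leave the patient out. Section 3.10.1 itself accepts that a discharged patient may later develop radiological changes that meet the progression definition, so the first option is hard to defend. The second keeps patients with early events while losing event-free patients.

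The scale is also wrong. A Cox model has no intercept; the counterpart is the baseline survival function, which Stage 1 does not mention. A slope on the logit scale is not a slope on the log-hazard scale, yet Stage 2 continues with hazard ratios.

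At stake are the absolute 5- and 10-year risks from the updated model. Updating the model is a listed secondary objective, and the introduction presents IMPACT as a tool to guide monitoring.

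**Working it through.** **1. The plan's own figure.** Section 3.4 asks for 100 events at a 10% progression risk: 100 / 0.10 = 1000 patients, as stated. At 1500 patients, 1500 × 0.10 = 150 events. Neither figure depends on Stage 1. The 10% is given without a time horizon; using it below as a 10-year risk is an assumption.

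**2. Bias from incomplete follow-up, by hand.** Let p be the true 10-year risk and q the share of censoring times before year 10 (assumed; the protocol gives none). Take constant, independent hazards h = −ln(1−p)/10 and c = −ln(1−q)/10.

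- Censored counted as non-events: A = h/(h+c) × [1 − (1−p)(1−q)]. The mean fitted risk of a logistic model with an intercept equals this observed proportion.
- Censored dropped: A / [A + (1−p)(1−q)].

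With p = 0.10, h = 0.01054. For q = 0.40, c = 0.05108, so A = 0.1710 × (1 − 0.54) = 0.0787, or 7.9%. Dropping gives 0.0787 / (0.0787 + 0.54) = 0.127, or 12.7%. For q = 0.10, c = h, so A = 0.5 × (1 − 0.81) = 0.095, or 9.5%; dropping gives 0.095 / 0.905 = 10.5%.

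**3. The same check with varying patient risk.** Simulation with 200,000 patients per scenario, proportional hazards, linear predictor SD 1, true Cox slope 1 and independent exponential censoring (all assumed). Mean risks, for a true 10-year risk of 10.0% (5-year 5.3%):

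| Censoring by year 10 | 10-year Kaplan-Meier | 10-year logistic, non-event | 10-year logistic, dropped | 5-year logistic, non-event | 5-year logistic, dropped |
|---|---|---|---|---|---|
| 0% | 10.0% | 10.0% | 10.0% | 5.3% | 5.3% |
| 20% | 10.0% | 9.0% | 10.9% | 5.0% | 5.5% |
| 40% | 9.9% | 7.9% | 12.4% | 4.7% | 6.0% |
| 60% | 9.9% | 6.6% | 14.7% | 4.3% | 6.6% |

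For a true 10-year risk of 20%, the same censoring levels (20%, 40%, 60%) give 18.2%, 15.9% and 13.7% with non-event coding, and 21.8%, 23.8% and 27.7% with dropping. Kaplan-Meier stayed within 0.2 percentage points of the truth in every scenario.

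**4. Scale, with no censoring at all.** Under a Cox model p = 1 − exp(−H), where H = H0 × exp(linear predictor). Then logit p = ln(exp(H) − 1), and its derivative with respect to the linear predictor is H / (1 − exp(−H)) = −ln(1−p)/p, which always exceeds 1:

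- p = 10%: 0.1054 / 0.10 = 1.05
- p = 20%: 0.2231 / 0.20 = 1.12
- p = 30%: 0.3567 / 0.30 = 1.19

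Spread in the linear predictor raises these. The simulated logistic slopes at 10 years without censoring were 1.10, 1.20 and 1.26. The Cox slope across all scenarios was 0.98 to 1.03.

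**The case against.** Several points on the other side stand.

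- **Reach.** Stage 1 is conditional and serves a secondary objective. The primary validation does not use it, and section 3.10.3 says the analysis plan will be reviewed before the final analysis.
- **Size.** Diagnoses in 2009–2010, with a timeline into late 2021, allow about ten years of potential follow-up. Records of discharged patients are searched up to data entry. Censoring may therefore be light, and at 10% the error is only about half a percentage point (step 2).
- **Complete follow-up.** With no censoring the mean logistic risk is right. Regression on the logit of the predicted risk, instead of the linear predictor, gave a slope of 0.99–1.00 in a separate check. But Stage 1 names the linear predictor.
- **Death and intervention.** The competing-risk analysis of progression treats these as competing events. For a cumulative-incidence target, a patient who dies before progressing is correctly a non-event. The bias concerns the Kaplan-Meier target and patients whose status at the horizon is unknown.
- **Hazard ratios.** Multiplying the Cox coefficients by the Stage 1 slope still yields hazard ratios, so Stage 2 can be run; they would be mis-scaled.

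A reader might also infer more than the protocol supports:

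- *That the slope above 1 would make a sound model look miscalibrated.* Section 3.10.1 judges calibration by predicted against Kaplan-Meier risk and by the Brier score, before Stage 1 begins.
- *That Stage 1 is a wrong response to poor discrimination because rescaling preserves ranks.* The trigger opens a four-stage procedure, and Stage 2 changes the predictors and reassesses discrimination.
- *That the risk groups and follow-up costs would be distorted.* The protocol gives no risk-group cut-offs, and section 3.10.4 does not say that the recalibrated model is the one costed.

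**Conclusion.** The point holds for the recalibration step. As written, Stage 1 applies a method without a horizon or censoring rule to a time-to-event model, at odds with section 3.10.1 and with the hazard-ratio scale of Stage 2. The direction of the error depends on a coding choice that the protocol leaves open. For a true 10-year risk of 10%, the assumed range runs from 9.0% or 10.9% (20% censoring) to 6.6% or 14.7% (60%). These figures rest on independent censoring, a linear predictor SD of 1 and assumed censoring shares; the true share is not in the protocol. The slope mismatch needs no censoring assumption. This should be corrected before any recalibration is run, but it does not threaten the primary objective.

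**What to change.** Replace the logistic sentence in Stage 1 with wording such as:

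> Fit a Cox model in the validation data with the IMPACT linear predictor (a) as an offset, re-estimating baseline survival at 5 and 10 years, and (b) as the only covariate, estimating the calibration slope and then baseline survival.

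Replace the reference to an intercept with baseline survival. A censoring-weighted or pseudo-value regression at each horizon is an acceptable alternative if both horizons and the weighting or pseudo-value method are stated. The cost is a few lines of text; the data and sample size stay the same, and standard survival software suffices.

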2.2. Secondary objectives

- To update the parameters of the prognostic model IMPACT if measures of external validation demonstrate a poor fit
- To determine the growth patterns of incidental meningiomas
- To examine the MRI and pathology features of meningiomas subject to surgical resection
- To determine the risk of post-intervention complications and tumour recurrence/growth for meningiomas subject to surgery, stereotactic radiosurgery, or fractionated radiotherapy
- To assess the economic implications of stratifying follow-up according to risk of disease progression

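### Stage 1 of the model update rescales all IMPACT weights by one common factor, and no later stage states that individual coefficients are re-estimated

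*Protocol*

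**What the plan says.** Protocol section 2.2 gives the secondary objective as follows: "To update the parameters of the prognostic model IMPACT if measures of external validation demonstrate a poor fit". Section 3.10.2 sets the trigger: "If calibration and discrimination measures of external validation demonstrate a poor fit, the model will be recalibrated and adjusted using the data of included patients".

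Four stages follow.

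- **Stage 1** states its aim, "The regression coefficients (including the intercept and slope) will be recalibrated", and its method: "This will be done using a logistic regression model fitted with the linear predictor as the only covariate".
- **Stage 2** takes the predictors of the recalibrated model, which are to be "removed in a stepwise manner by a non-automated criterion-based procedure starting with the variable with a hazard ratio closest to 1". Then: "After removal of this variable, the aforementioned measures of discrimination of calibration and discrimination will be reassessed to detect model improvement". A variable goes back in if performance is no better or is worse.
- **Stage 3** is a bootstrap assessment of internal validity.
- **Stage 4** adjusts the comorbidity and performance status strata.

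Section 1.1 describes the original function as a Cox model with four MRI parameters: volume, hyperintensity, peritumoural signal change and proximity to critical neurovascular structures. The protocol does not give their coefficients.

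**The concern.** The aim and the method of Stage 1 do not match. The aim speaks of regression coefficients; the method estimates one slope for the whole score. If one predictor carries a different weight in the new cohort, a common slope spreads that error over all four predictors and does not locate it.

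The update also starts when discrimination is poor, yet Stage 1 cannot improve discrimination. Stage 2 offers only two values for each weight, the scaled one or zero. A predictor that matters, but more or less than in the development data, would leave its carriers with wrong predicted risks in a model reported as updated. IMPACT is meant to stratify monitoring, so subgroup risks are what users would act on.

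**Working it through.** **1. The plan's own figure.** Section 3.4 asks for 100 events at a 10% progression risk: 100 / 0.10 = 1000 patients, which reproduces. The minimum of 1500 gives 1500 × 0.10 = 150 expected events if the risk holds. The extra 500 are there to cover variability and losses, so the planned minimum remains 100.

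**2. Stage 1.** Let LP = Σ bⱼxⱼ. The fitted model is logit(p) = a + s·LP, so each weight becomes s·bⱼ and the ratio of two weights, s·bⱼ / s·bₖ = bⱼ / bₖ, is unchanged. For s > 0 the ranking of patients is unchanged, so rank-based measures such as the C-statistic, the D-statistic and the empirical AUC cannot move. An AUC estimator that plugs in predicted risks could shift numerically, but no patient changes place. All this holds in any regression family.

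**3. Stage 2 order.** Scaling turns each hazard ratio HRⱼ into HRⱼ raised to the power s. With assumed weights 0.8, 1.0, 1.0 and 0.7, the hazard ratios are 2.23, 2.72, 2.72 and 2.01; with s = 0.7 they become 1.75, 2.01, 2.01 and 1.63. The order is the development order, unless a refit that the text does not state takes place first.

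**4. Size.** The simulation used a logistic model, 1500 patients, 10% events and 150 runs per scenario, with performance measured on 20,000 new patients per run. The four weights are those in step 3. The first predictor was standard normal and the other three binary with prevalence 30%, 15% and 40%, all independent. These inputs are assumptions. The true weight of the 30% predictor was moved away from its published value of 1.0. "Drop" refits intercept and slope on the remaining score. Ratio means predicted over true risk among carriers of that predictor.

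| True weight | Weight after Stage 1 | Re-estimated weight | AUC: Stage 1 / drop / re-estimate | Ratio: Stage 1 / drop / re-estimate | Runs where dropping raised apparent AUC |
|---|---|---|---|---|---|
| 1.0 | 1.00 | 1.00 | 0.764 / 0.736 / 0.762 | 0.99 / 0.61 / 0.99 | 0.7% |
| 2.0 | 1.22 | 2.00 | 0.802 / 0.721 / 0.818 | 0.77 / 0.44 / 1.00 | 0% |
| 0.5 | 0.89 | 0.49 | 0.742 / 0.741 / 0.744 | 1.21 / 0.77 / 1.00 | 50% |
| 0.0 | 0.80 | −0.02 | 0.719 / 0.742 / 0.739 | 1.52 / 1.00 / 1.00 | 96% |
| −0.5 | 0.71 | −0.53 | 0.697 / 0.741 / 0.744 | 2.01 / 1.37 / 1.00 | 100% |

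AUC before and after Stage 1 was identical in every row. Keep-or-drop works at zero, helps only partly with the wrong sign, and fails for a doubled or halved weight. A second simulation at 1500 patients, with other assumed weights and prevalences, agreed: 1.18 (kept) or 0.73 (dropped) when halved and 0.82 or 0.42 when doubled, against about 1.00 with re-estimation.

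**5. Which test to use.** A tempting test adds the four predictors to a model with LP as an offset. That fixes the slope at 1, so the comparison is with the original model and not with the Stage 1 result. Under an assumed uniform slope of 0.64, which Stage 1 corrects fully, the offset test rejected in 92.5% of runs in one simulation and about 95% in another. The comparison with a free slope rejected in 3.5% and about 7%.

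**The case against.** The strongest reply is that the text does not rule out re-estimation. Stage 1 names the regression coefficients as its target. Stage 2 ranks by hazard ratio, which a one-covariate logistic fit does not produce. Section 3.10.1 adds: "Model assumptions will be tested by examination of Schoenfeld residuals, and influential observations will be examined using DFBETA panels". Those checks suggest a Cox fit to the new data. Section 3.10.3 says the analysis plan will be reviewed before the final analysis, and a refit rule is ordinary detail for a separate plan.

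Much of this stands. A reader might infer that Stage 2 drops predictors without refitting the rest; the protocol is silent on this and does not say so. A reader might also infer that a wrong weight can never be found or corrected. That fails for a predictor with no effect, where removal restores both discrimination and calibration, and removal also detects a wrong sign. The Schoenfeld and DFBETA sentence shows only that the model being checked is unnamed.

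Nor do the documents show that a predictor-specific shift is the likeliest failure. Signal is read against contralateral grey matter (section 3.8.2), with a video manual and a required assessment score of 100% (section 3.9).

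The gain in discrimination can also be small: 0.742 to 0.744 for the halved weight, where the sampling SD of C at 1500 patients was about 0.022 in a separate simulation. The case for re-estimation there rests on subgroup calibration.

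What the reply does not reach is the stated Stage 1 method. It is fixed in the protocol and does not do what its own first sentence says. No result of the section 3.10.1 checks is carried into section 3.10.2.

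**Conclusion.** The point holds in this form. Stage 1 as specified allows only a common scaling. It cannot alter relative weights or improve the ranking of patients, although poor discrimination is part of the trigger. Stage 2 then chooses between the scaled weight and zero, and leaves open whether the remaining coefficients are refitted. No stage states re-estimation, despite the objective in section 2.2.

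The Stage 1 result is algebra and needs only a positive slope. The sizes rest on assumed weights, prevalences and independence of predictors, with complete binary outcomes. On those assumptions, predicted risk in carriers is about 20% too high or 23% too low for a halved weight, and 23% or 56% too low for a doubled one, depending on whether the predictor is kept or dropped. If the weights transport well or all shrink alike, Stage 1 suffices and nothing is lost.

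**What to change.** Insert a step between Stages 1 and 2 of section 3.10.2:

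- Fit a Cox model to the validation data with the IMPACT predictors, coded as in development, and their coefficients free.
- Compare it by likelihood ratio test with a Cox model on the same data that has the linear predictor as sole covariate and a free slope. Degrees of freedom are the number of coefficients minus 1 (4 − 1 = 3 if each predictor takes one). Do not use an offset model with the slope fixed at 1.
- If the test rejects, use the re-estimated coefficients and baseline survival, shrunk by the Stage 3 bootstrap. Otherwise keep the Stage 1 recalibration.
- State that the remaining coefficients and the baseline are refitted after any Stage 2 removal.

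The cost is rewording and one extra model fit on data already collected. The downside is added estimation error, limited by shrinkage; when the published weights were right, unshrunk re-estimation gave AUC 0.762 against 0.764. With 100 to about 150 events there are 100 / 4 = 25 to 150 / 4 = 37.5 per coefficient, and fewer if a predictor needs several categories.
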